## **STATISTICAL ANALYSIS PLAN**

### **Primary Endpoint**

Need of mechanical ventilation first 72 hours in life

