## **BACKGROUND**

Respiratory distress syndrome (RDS) is the leading cause of respiratory failure in preterm infants. The incidence and severity of RDS are inversely related to the gestational age of the newborn. Despite recent improvements in neonatal care, RDS still remains as major cause of morbidity and mortality in preterm infants. Exogenous surfactant treatment is known to reduce mortality and morbidity in premature infants with RDS.

Surfactant therapy should be performed by health care-givers who are experienced in intubation and MV of the newborn. Most premature infants can tolerate extubation after application of surfactant and continue with CPAP or nasal intermittent positive pressure ventilation (NIPPV) so INSURE (INTubate, SURfactant, Extubate) can be preferred as the surfactant application method. Researchers have thus been looking for less invasive ways to administer surfactant without the need for intubation. A method, called LISA (less invasive surfactant administration) in which a soft flexible catheter instead of an endotracheal tube is placed in the trachea under direct laryngoscopy using Magill forceps and the surfactant is applied. The method, non invasive ventilation (NIV) continues during the surfactant application. All meta-analyses reviewing LISA methods showed that LISA reduced the need for MV in the first 72 hours of life. LISA method can be used with NCPAP or NIPPV.

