## **GOALS OF THE STUDY**

1. To compare the effectiveness of NIPPV versus NCPAP in preterm infants with RDS.
2. To evaluate the development of apnea, bradycardia, desaturation and surfactant reflux
3. To evaluate need of repeat surfactant dose
4. To evaluate need of mechanical ventilation within 72 hours following surfactant treatment
5. To evaluate duration of non invasive and invasive ventilation
6. To evaluate long term outcomes such as bronchopulmonary dysplasia, retinopathy of prematurity, intraventricular hemorrhage, necrotizing enterocolitis.

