### **Standard procedures after randomization**

- Patients in the NCPAP group will start CPAP with an initial pressure of 6 cm H2O, while patients in the NIPPV group will be applied 6 cm H2O pressure, 15-20 cm H2O peak inspiratory pressure, and NIPPV at a rate of 20-30 per minute.
- In both groups, the surfactant will be administered at a dose of 200 mg / kg / dose through a special catheter named Lisacath, by visualizing the vocal cords by the responsible and experienced physician in each center.
- In cases with fractional inspired oxygen FiO2 >0.3, the second dose of surfactant will be administered within the first 12 hours at least 6 hours after the first dose.
- "Study Algorithm" is presented.
- Data such as possible adverse effects, complications related to the procedure, prenatal, natal and postnatal demographic characteristics, need for repeat dose surfactant, intubation requirement and time, follow-up NCPAP / NIPPV settings will be recorded.

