**Visit 4: (7nd days)**

- **Neonatal outcomes 1**
  - Need of mechanical ventilation and entubation, time of entubation
  - Need of repeat surfactant treatment

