## **SAMPLE SIZE JUSTIFICATION**

With the power analysis performed for the study, the number of samples required to determine a 15% difference in terms of going to mechanical ventilation between both groups was calculated as 170, with a power of 80% for each group. In the study, 15% of the difference in babies 26 weeks and younger; Under the assumption that the difference will be 10% for babies older than 26 weeks, it is planned to have babies aged 26 weeks and younger than 26 weeks equally in each group.

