### **Secondary Endpoints**

Development of bronchopulmonary dysplasia and other prematurity-related morbidity

All analyses will be performed using per-protocol population as well as intention-to-treat population.

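### Does goal 4, which counts 72 hours from surfactant, leave the primary ventilation endpoint ambiguous?

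*Combined protocol and SAP*

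**What the plan says.** The Primary Endpoint section of the statistical analysis plan reads "Need of mechanical ventilation first 72 hours in life". It is the only outcome definition labelled primary. The Background describes the evidence on the surfactant method with the same clock: "LISA reduced the need for MV in the first 72 hours of life".

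Goal 4, one of six numbered and unranked goals, reads "To evaluate need of mechanical ventilation within 72 hours following surfactant treatment". It does not name a dose, although the section on procedures after randomisation foresees a repeat: "the second dose of surfactant will be administered within the first 12 hours at least 6 hours after the first dose".

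The sample size section is built on a "15% difference in terms of going to mechanical ventilation between both groups" and gives no time window. The Secondary Endpoints section lists only "Development of bronchopulmonary dysplasia and other prematurity-related morbidity".

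For data capture, the procedures section records "need for repeat dose surfactant, intubation requirement and time", and the day 7 visit records "Need of mechanical ventilation and entubation, time of entubation".

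**The concern.** One outcome appears with two clocks. Infants may enter up to 6 hours after birth, so a window that starts at surfactant ends later than one that starts at birth. An infant dosed at 6 hours and first ventilated at 75 hours of age is a non-event under the primary endpoint (the window closes at 72 hours) and an event under goal 4 (it closes at 6 + 72 = 78 hours). The windows also differ at the start. An infant intubated after randomisation but before surfactant is an event under the primary endpoint, while goal 4 has no rule for that infant.

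Neither the secondary endpoint list nor the sample size section settles the matter. If the two versions had equal standing, the more favourable one could be reported once the data were known. With about 85 infants per arm, one or two reclassified infants can matter near a significance threshold.

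**Working it through.** **Which text governs.** The primary endpoint section carries the label and states its clock, and the Background agrees with it. Goal 4 is never called an endpoint. Its absence from the secondary list says nothing particular about it, because that list also does not name the subjects of goal 2 (procedural events and reflux), goal 3 (repeat dose) or goal 5 (duration of support).

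**Which dose.** Visits 2 and 3 are set at 1 and 4 hours after surfactant, the appendix schedule has a single treatment hour 0, and repeat dosing has its own goal. The first dose is the natural reading of goal 4.

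**The plan's own figure.** The 170 in the sample size section cannot be used to infer a window. It states no control rate, alpha or sidedness, so the figure can be neither confirmed nor refuted. With an assumed two-sided alpha of 0.05 and no continuity correction, 85 per arm for a 15-point reduction fits a control rate near 22%.

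**Size of the difference.** Inputs from the documents: a 72-hour window, entry by 6 hours of age, and 170 infants randomised 1:1, so 170 / 2 = 85 per arm. Assumed: the proportion p ventilated by 72 hours in each arm, a constant hazard, and the same offset d (hours from birth to the dose that starts the clock) for every infant.

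- Hazard: h = −ln(1 − p) / 72. For p = 0.30, h = 0.00495 per hour. For p = 0.15, h = 0.00226 per hour.
- Extra events between 72 and 72 + d hours: (1 − p) × (1 − exp(−h × d)).
- At d = 6: 0.70 × (1 − exp(−0.0297)) = 2.05 points, and 0.85 × (1 − exp(−0.0135)) = 1.14 points.

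| Offset d | Extra events, 30% arm | Extra events, 15% arm | Shift in difference | Net infants (× 85) |
|---|---|---|---|---|
| 3 h | 1.03 points | 0.57 points | 0.46 points | 0.39 |
| 6 h | 2.05 points | 1.14 points | 0.91 points | 0.77 |

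At d = 6 with other rates, the shift is 1.07 points for 20% versus 5%, 0.72 for 40% versus 25%, and 0.51 for 50% versus 35%. The largest of these is 0.0107 × 85 = 0.91 infants.

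**If the clock started at the second dose.** The 12-hour limit on that dose has no stated origin. Counted from birth, the offset reaches 12 hours. Counted from a first dose at 6 hours, it reaches 6 + 12 = 18 hours. At 30% versus 15%, and with every infant re-dosed, the shifts are 4.04 − 2.27 = 1.77 points (1.5 infants) and 5.97 − 3.38 = 2.59 points (2.2 infants). At 20% versus 5% they are 2.11 and 3.13 points. These are extremes on a reading that the visit schedule does not support.

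**The case for a change.** The strongest argument for a change is that goal 4 is the only goal that states the ventilation outcome, and it disagrees with the analysis plan. No blinding is described that would limit a late choice between versions. Dropping infants intubated before surfactant, as goal 4 could be taken to allow, would be an exclusion after randomisation, at a point when the arms are already on different support. Aligning the wording would cost a line or two.

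Part of this stands. The two texts do differ, nothing reconciles them, and goal 4 is loosely worded. The rest carries less weight. Reporting goal 4 as the primary result would be a visible departure from a labelled endpoint. The intention-to-treat analysis that the plan specifies keeps every randomised infant, and an infant intubated early is simply an event under the primary definition. The early group cannot be sized from the documents, but it is limited to intubations between randomisation and surfactant, because a need for ventilation already excludes an infant at entry. The remedy would keep the same primary clock, so the primary result would be the same with or without it.

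**Conclusion.** The mismatch is real, but it is a slip of wording in a goal and does not make the primary endpoint ambiguous. An analyst following the plan counts ventilation up to 72 hours from birth and has the intubation times to do so. Reading goal 4 from the first dose, the two clocks differ by less than one infant net between arms: 0.9 points at 30% versus 15%, and 0.5 to 1.1 points over the other rates tried. That rests on assumed event rates, a constant hazard, 85 infants per arm, and a first dose no later than the 6-hour entry limit, which the documents set for entry and not for dosing. It covers only the end of the window. Tidying the goal or adding a second-window analysis would leave the primary analysis and its conclusion as they are, so no change is called for.

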### **Secondary Endpoints**

Development of bronchopulmonary dysplasia and other prematurity-related morbidity

All analyses will be performed using per-protocol population as well as intention-to-treat population.

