## STUDY SUMMARY

Title	Comparison of efficacy of less invasive surfactant treatment under nasal CPAP and nasal IPPV in premature babies: CURLISPAP STUDY
Methodology	Randomized, controlled trial
Study Duration	Estimated duration for the main protocol (e.g. from start of screening to last subject processed and finishing the study) is approximately 2.0 years
Study Center(s)	Multi-center (Uludag University Hospital Marmara University Hospital, Gazi University Hospital, Ankara University Hospital Başakşehir Çam ve Sakura City Hospital and Dokuz Eylül University Hospital)
Objectives	
Primary Objective: To compare the effectiveness of nasal intermittent positive pressure ventilation (NIPPV) versus nasal continuous positive airway pressure (CPAP) in preterm infants with respiratory distress syndrome (RDS).
 
Secondary Objectives: To evaluate short and long term neonatal outcomes such as bronchopulmonary dysplasia, duration of mechanical ventilation, retinopathy of prematurity and intraventricular hemorrhage.

Number of Subjects	170 randomized patients in two arms; NCPAP and NIPPV group
Diagnosis and Main Inclusion Criteria	
Inclusion Criteria
 
 
• Gestational age 24 -29 week
 
• Clinical and radiological diagnosis of RDS
 
• Born in a hospital with a study center
 
• Spontaneous breathing
 
• Within the first 6 hours
 
• Non-invasive ventilation and FiO2 requirement >0.30
 
• Parental consent
 
 
Exclusion Criteria
 
 
• Major congenital malformations
 
• Need of mechanical ventilation
 
• Need of entubation in delivery room
 
• Air weak syndrome
 
• No parental consent
 

Study Product, Dose, Route, Regimen	
 
• NCPAP Group: Will receive standard NCPAP protocol
 
• NIPPV Group: Will receive standard NIPPV protocol
 
• SURFACTANT: As a surfactant preparation, Curosurf® will
 

	be applied in all patients with a standard dose of 200 mg / kg and a special catheter Lisacath® as a standard in all of patients.
--	---

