## **REASONS FOR WITHDRAWAL OR TERMINATION**

Parents may be discontinued from the study at any time, for any reason, specified or unspecified, and without prejudice

The following is a list of possible reasons for study treatment discontinuation:

- Screening Failure
- Parents withdrawal of consent
- Lost to follow-up
- Subject death before 36 week gesatational age

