**Visit 6: (discharge date)**

- **Neonatal outcomes 2**
  - Duration of total NCPAP, NIPPV, entubation and oxygen
  - Intraventricular hemorrhage
  - Bronchopulmonary dysplasia
  - Necrotizing enterocolitis
  - Retinopathy of prematurity
  - Sepsis
  - Advers events

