## **ASSESSMENT OF SAFETY**

Adverse events (AE) will be monitored and collected by the study team. For each AE, a detailed explanation will be obtained from the subject and subject's medical record. All AEs will be recorded on the CRFs.

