### **Definition of Severe Adverse Event (SAE)**

An AE is defined as any unanticipated medical occurrence regardless to relationship of the investigative arm of the trial.

- Death
- Prolong hospitalisation

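### BPD is a secondary endpoint without death, and no endpoint names mortality, so a mortality difference can make the arm with more deaths look better on BPD

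*Combined protocol and SAP*

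**What the plan says.** The Secondary Endpoints section of the SAP names "Development of bronchopulmonary dysplasia and other prematurity-related morbidity". It adds: "All analyses will be performed using per-protocol population as well as intention-to-treat population". The primary endpoint is ventilation within 72 hours.

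The Study Summary's secondary objectives read "To evaluate short and long term neonatal outcomes such as bronchopulmonary dysplasia, duration of mechanical ventilation", followed by retinopathy and intraventricular hemorrhage. Goals of the Study adds necrotizing enterocolitis and "To evaluate duration of non invasive and invasive ventilation". Neither list names death. Visit 6 records "Duration of total NCPAP, NIPPV, entubation and oxygen". Visit 5, at 36 weeks, offers five respiratory-support categories, none of which fits a baby who has died.

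Death appears in two other places. Reasons for Withdrawal or Termination includes "Subject death before 36 week gesatational age" as a reason for stopping study treatment. The SAE definition under Assessment of Safety lists death, with "All AEs will be recorded on the CRFs" and notification of the sponsor within one working day. Deaths are therefore foreseen and captured, but no efficacy comparison uses them.

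**The concern.** The babies are 24 to 29 weeks at birth, and BPD status is not available for one who dies before 36 weeks. Requiring intention-to-treat keeps such a baby in the population but does not give the baby an outcome. Two rules are open to the analyst:

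- Count deaths as no BPD. Each death of a baby who would have developed BPD then lowers that arm's BPD rate.
- Leave deaths out. The arm with more deaths then looks better if the babies who died were at higher BPD risk than the rest.

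Under either rule, a reader of the secondary results could see a BPD advantage without the deaths behind it. The rule could also be chosen after the results are known. Support durations raise a related question, since death ends support and no rule covers babies who die.

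**Working it through.** **Inputs from the documents.** 170 babies in two arms (Study Summary), allocated 1:1 (Methods and Study Schedule), so 85 per arm. The documents give no mortality, BPD or duration figures, so there is no figure of the plan's own to reproduce. Every rate below is assumed.

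**Model.** H is the arm with more deaths and L the arm with fewer; either may be NCPAP or NIPPV. Let mH and mL be the mortalities, b the BPD risk in babies who would survive in either arm, and q the BPD risk in the extra survivors, who live in L but would have died in H. No baby survives only in H, and the mode has no other effect on BPD. Any difference then comes from mortality alone.

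- Survivors only: H = b; L = [(1 − mH)b + (mH − mL)q] / (1 − mL). L − H = (mH − mL)(q − b) / (1 − mL).
- Deaths as no BPD: H = (1 − mH)b; L = (1 − mH)b + (mH − mL)q. L − H = (mH − mL)q.
- Death or BPD: H = mH + (1 − mH)b; L = mL + (1 − mH)b + (mH − mL)q. L − H = (mH − mL)(q − 1).

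**Middle case.** mH = 0.15, mL = 0.10 (0.15 × 85 = 12.75 and 0.10 × 85 = 8.5 expected deaths), b = 0.30, q = 0.80. Here (1 − mH)b = 0.255 and (mH − mL)q = 0.040.

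| Comparison | H | L | L − H | SE |
|---|---|---|---|---|
| BPD, survivors only | 30.0% | 0.295/0.90 = 32.8% | +2.8 points | 7.6 |
| BPD, deaths as no BPD | 25.5% | 29.5% | +4.0 points | 6.8 |
| Death or BPD | 40.5% | 39.5% | −1.0 point | 7.5 |

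Each SE is √[pH(1 − pH)/nH + pL(1 − pL)/nL]. The n values are 72.25 and 76.5 for survivors (85 × 0.85 and 85 × 0.90) and 85 and 85 otherwise.

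**What a shift of this size does.** The chance that H shows the numerically lower BPD rate rises from 50% to Φ(2.78/7.61) = 64% for survivors only, or Φ(4.0/6.84) = 72% with deaths as no BPD. The chance of a nominally significant result for H (two-sided 5%, so 2.5% with no shift) becomes Φ(−1.96 + 0.365) = 5.5% or Φ(−1.96 + 0.585) = 8.5%.

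**When it vanishes or reverses.** All three differences are zero if mH = mL. The survivors-only shift is also zero if q = b, and reverses if q < b.

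**A different model.** Suppose 30% of babies are frail (BPD 60%), the rest are not (BPD 20%), and all deaths are among the frail. With 5% vs 15% mortality, survivor BPD is 0.29/0.95 = 30.5% vs 0.23/0.85 = 27.1%, which favours the arm with more deaths. Death or BPD is 34% vs 38%, which favours the other arm.

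**Durations.** The raw mean is (1 − m)s + md, with s support days in survivors and d in babies who die. At 15% vs 10% mortality and s = 20:

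- d = 5: H 17.75 vs L 18.50 days, so H looks 0.75 days better.
- d = 40: H 17 + 6 = 23.0 vs L 18 + 4 = 22.0 days, so H looks 1.0 day worse.

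**The case against.** Several points on the other side stand.

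- **Deaths are not hidden.** A reader might infer that the trial fails to collect them or drops babies who die. The documents do not support that. Death is an SAE that goes on the CRF and to the sponsor, and the withdrawal section makes it a reason for stopping treatment, not for exclusion from analysis. What is missing is any requirement to compare mortality by arm or show it beside BPD.
- **BPD per randomized baby is a legitimate intention-to-treat quantity.** If the extra survivors develop BPD, their arm really does have more cases. That makes this rule a problem of interpretation rather than bias in the strict sense, and mortality shown alongside largely resolves it. Leaving deaths out, for its part, would depart from the usual meaning of intention-to-treat.
- **The lists of outcomes are open-ended.** Wording such as *such as* could admit mortality, but it does not commit anyone to reporting it.
- **Raw durations are not a stated analysis.** A reader might infer that the plan compares them. The endpoint list contains no duration; the objectives and goals only say durations will be evaluated, and Visit 6 is a list of items to record. The gap is the absence of a rule.
- **Large shifts can be produced, but only at the extremes.** With 30% vs 20% mortality, b = 0.30 and BPD in every extra survivor, the survivors-only shift is (0.21 + 0.10)/0.80 − 0.30 = 8.75 points (10.0 at b = 0.20, 7.5 at b = 0.40). With deaths as no BPD it is 0.10 × 1 = 10.0 points. Nothing in the documents makes these cases likely.
- **The composite adds little discrimination.** In the middle case it separates the arms by 1.0 point, and H still looks better Φ(−1.0/7.51) = 45% of the time. Its direction follows from its definition and is not evidence. Mortality by arm is the most useful addition.

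**Conclusion.** The concern holds in a limited form. BPD stands without death, no endpoint, objective or goal names mortality, and no rule says how a baby who dies before 36 weeks is counted. A mortality difference can therefore favour the arm with more deaths on BPD. With deaths as no BPD this follows whenever any extra survivor would develop BPD. With survivors only it also needs the babies who died to be at higher BPD risk.

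Under the assumed middle case the shift is 2.8 to 4.0 points, below one standard error at 85 per arm. It is modest beside chance variation and cannot be sized from the documents. Durations carry the same caution without a predictable sign.

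The documents do not support the inference that NIPPV, or NCPAP, is favoured: the effect can go either way. This point also does not extend to the primary endpoint. It is a cheap improvement to the secondary analysis, not a flaw that threatens the trial's main conclusion.

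**What to change.** In the Secondary Endpoints section, before outcome data are seen:

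1. Add death before 36 weeks or BPD as a secondary endpoint in all randomized babies, using the trial's own BPD definition, which the plan should state.
2. Show mortality by arm and BPD among survivors beside it, each with its denominator.
3. Report support durations in survivors next to mortality by arm. Use days alive and free of support only if support days within one fixed window can be derived from the collected data. Visit 6 records totals, and a window ending at 36 weeks would run from about 43 days (birth at 29 6/7 weeks) to 83 days (birth at 24 1/7 weeks).
4. Leave the primary endpoint unchanged.

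The cost is a few lines of SAP text and a few table rows. No extra patients are needed, and the deaths are already captured. The downside is that the composite mixes two outcomes of different weight, so its components must always be shown with it.

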## **ASSESSMENT OF SAFETY**

Adverse events (AE) will be monitored and collected by the study team. For each AE, a detailed explanation will be obtained from the subject and subject's medical record. All AEs will be recorded on the CRFs.

### **Definition of Severe Adverse Event (SAE)**

An AE is defined as any unanticipated medical occurrence regardless to relationship of the investigative arm of the trial.

- Death
- Prolong hospitalisation

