## **POTENTIAL BENEFITS AND RISKS TO PATIENTS**

The study includes routine treatment protocols. LISA is one of the standard surfactant treatment applications. Possible complications during surfactant treatment such as apnea, bradycardia, desaturation and surfactant reflux will be followed.

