### **Surfactant treatment**

- Surfactant preparation, standard Curosurf® will be applied at a dose of 200 mg / kg and a special catheter Lisacath® as standard
- Surfactant application with the LISA method, which is routinely used in the world and in our country, was well tolerated in most cases. Although sudden decreases in heart rate for less than 10 seconds can be seen in approximately half of the cases during surfactant administration by LISA method, such short-term changes in heart rate are not considered harmful for the baby. In current studies, problems such as airway damage or damage to the vocal cords have not been encountered. The treatment team will apply treatments that will reduce pain and eliminate possible discomfort when necessary.
- Surfactant reflux may occur during less invasive surfactant application.
- Surfactant reflux will be scored according to the status of reflux in the catheter, in the mouth and in the nose.

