### **Relationship to Study Products**

For all collected AEs, the clinician who examines and evaluates the participant will determine the AE's causality based on temporal relationship and his/her clinical

judgment. The degree of certainty about causality will be graded using the categories below.

**Definitely:** The relationship of the AE and the study device or the study procedure can definitely be established.

**Probably:** While a clear relationship to the study device or to the study procedure cannot be established, the AE is associated with an expected AE or there is no other medical condition or intervention, which could explain the occurrence of such an event.

**Possibly:** There is no clear relationship between the AE and the study device or study procedure; however, one cannot definitely conclude that there is no relationship.

**Unrelated:** There is no relationship between the AE and the study device or study procedure.

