### **SAE Reporting**

In the case of a SAE, the Investigator must notify the Sponsor within 1 working day after the Investigator first learns of the event.

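### The adverse event definition covers only unanticipated occurrences and no separate SAE definition exists, so AE classification of anticipated events is inconsistent and a survived life-threatening event need not be notified promptly

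*Combined protocol and SAP*

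**What the plan says.** The section Definition of Severe Adverse Event (SAE) has one sentence and two bullets. The sentence defines an AE, not an SAE: "An AE is defined as any unanticipated medical occurrence regardless to relationship of the investigative arm of the trial". The bullets are death and "Prolong hospitalisation". No other section of the available text defines either term.

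The sections that depend on this definition are:

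- Assessment of Safety: "All AEs will be recorded on the CRFs".
- Relationship to Study Products: causality is graded for collected AEs, and the second category applies where "the AE is associated with an expected AE or there is no other medical condition or intervention" that could explain the occurrence.
- SAE Reporting: in the case of an SAE, "the Investigator must notify the Sponsor within 1 working day after the Investigator first learns of the event".

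Other sections bear on what is anticipated:

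- Potential Benefits and Risks to Patients: "Possible complications during surfactant treatment such as apnea, bradycardia, desaturation and surfactant reflux will be followed".
- Surfactant treatment: "sudden decreases in heart rate for less than 10 seconds can be seen in approximately half of the cases". The same sentence adds that such short changes are not regarded as harmful.
- Adverse reactions: the protocol expects no adverse outcome and no risk.

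**The concern.** Two things depend on this definition. The first is the AE table by arm. If unanticipated is a condition for being an AE, whether a desaturation during surfactant administration is recorded and graded as an AE depends on how each centre reads the word. The Study Summary lists six centres. Differences in reading between centres would add noise to the AE comparison, and the causality grades would cover an unclear subset of events.

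The second is prompt notice to the sponsor. The one-working-day rule applies only to SAEs, and the only stated SAE criteria are death and a longer stay. An infant who nearly dies during the procedure and recovers with no visible effect on length of stay meets neither. In the available text, the other stated oversight is the monthly review by the study team under Data Monitoring.

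**Working it through.** No sample-size or error-rate calculation applies. The check is to take event types through the rules as written.

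| Event | AE under the definition? | Causality graded? | SAE, with one-working-day notice? |
|---|---|---|---|
| A. Anticipated procedural event, no effect on stay | No, read literally; yes, if the causality scale's wording is followed | Only if it is an AE | No |
| B. Anticipated complication or prematurity morbidity that prolongs stay | Same conflict as A | Only if it is an AE | Yes on the bullet alone; unclear if an SAE must first be an AE |
| C. Unanticipated life-threatening event, survived, stay not prolonged | Yes, on the CRF | Yes | No |
| D. Unanticipated life-threatening event, stay prolonged | Yes, on the CRF | Yes | Yes, once the prolongation is recognised |

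**Rows A and B.** The definition and the causality scale cannot both be followed. If every AE is unanticipated, an expected AE cannot exist, yet the scale grades against one. The Adverse reactions section does not resolve this. Taken at its word, nothing is anticipated and almost any harm is an AE. Taken with Potential Benefits and Risks to Patients and Surfactant treatment, several events are anticipated and are not AEs. Three readings are open, and no text chooses among them.

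**Are these events lost?** No. Goal 2 in Goals of the Study names the same procedural events. Standard procedures after randomization records adverse effects and procedural complications. Surfactant treatment provides a reflux score. Visit 6 collects intraventricular haemorrhage, bronchopulmonary dysplasia, necrotizing enterocolitis, retinopathy, sepsis and adverse events. Unscheduled Visit and the Appendix grid include AE and complication checks. The inconsistency is in classification, grading and SAE route, not in capture.

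**Row C.** This is the gap in prompt notice. The event is on the CRF and graded, but SAE Reporting is not triggered.

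**Row D.** The safeguard is a longer stay, but longer than what is not stated. Eligible infants are 24 weeks 1 day to 29 weeks 6 days at birth and are treated within the first 6 hours of life. The schedule has a visit at 36 weeks before the discharge visit. Reading that as 36 weeks 0 days:

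- oldest eligible infant: 36w0d − 29w6d = 252 − 209 = 43 days (6 weeks 1 day);
- youngest eligible infant: 36w0d − 24w1d = 252 − 169 = 83 days (11 weeks 6 days).

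If infants stay in hospital until about the 36-week visit, as the visit order suggests, a longer stay caused by an event on day 0 may not be apparent for some 6 to 12 weeks. A notice that waits for that is not prompt.

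**The case against.** The strongest reply is that the trial follows these infants closely and loses little. An unanticipated life-threatening event is still an AE and goes on the CRF. If it prolongs the stay, it is an SAE and is notified within one working day. The anticipated procedural events and the prematurity morbidities are collected in their own right and can be compared by arm whatever they are called. The causality scale suggests that the authors did mean to include expected events. All of this stands, and it limits the point to classification, grading and the notice for row C, with the timing of row D.

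Three stronger readings are tempting, and the documents do not support them.

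- A reader might infer that anticipated and life-threatening harms go uncounted altogether. The collection sections listed above contradict this.
- A reader might apply the protocol's frequency for brief heart-rate falls to the whole sample and report the result as harms excluded. The protocol calls those falls harmless and follows bradycardia in any case, so the result would not be a count of lost harms.
- A reader might infer that a particular unlisted harm, such as air leak, escapes. No section names it in advance, so under the definition it is most naturally an unanticipated occurrence and therefore an AE. Whether to make it a named outcome is a separate choice of endpoint.

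It can also be said that a longer list of seriousness criteria is an outside convention. The point does not rest on one. It rests on what the stated rule does with a survived life-threatening event.

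**Conclusion.** The concern holds in a limited form. The definition is defective as written: it places an AE sentence under an SAE heading, conflicts with the causality scale, and has no reference for unanticipated because the Adverse reactions section disagrees with the sections that name complications. The AE label, causality grading and SAE route of anticipated events are therefore inconsistent. A life-threatening event that is neither fatal nor prolongs the stay does not trigger the one-working-day notice, and prolonged has no reference in this population.

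The size cannot be given as a number, because the documents state no rate for life-threatening events and no expected length of stay. The primary endpoint, need for mechanical ventilation in the first 72 hours, is not affected. The conclusion assumes that centres apply the written wording. Centres that already report more widely would reduce the practical effect, but the protocol would still not require it. The wording should be corrected because it bears on safety reporting and on uniform classification across six centres.

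**What to change.** Reconcile four sections: Adverse reactions, Definition of Severe Adverse Event (SAE), Relationship to Study Products, and SAE Reporting.

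1. Define an AE as any untoward medical occurrence, anticipated or not.
2. Define an SAE in its own sentence: death, a life-threatening event, lasting disability, or a hospital stay prolonged because of the event. The causal wording in the last criterion gives prolonged a reference.
3. State whether the prespecified procedural complications and the prematurity morbidities are classified as AEs, graded for causality and tabulated by arm. If some are to be reported only as outcomes, list them and say so.
4. Align the Adverse reactions statement with the complications named elsewhere.

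The cost is wording plus some extra AE entries and SAE notices. No added visit, procedure or sample-size change is needed.
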